A step further to conventional treatment is the use of a home-based approach allowing remote internet monitoring of treatment between office visits and hence better compliance. **(Hess et al., 2014)** In addition a video game version of the treatment is developed to make it more enjoyable for improving compliance. **(Foss et al., 2013)**. Moreover, dichoptic presentation can be achieved on the iPod device using a lenticular overlay screen. The advantage of using a lenticular overlay screen is that the luminance contrast is preserved **(Hess et al.; 2014)**

Aim of the work:

The aim of this work is to compare the gold standard occlusion therapy alone with dichoptic therapy

Patients and Methods:

Design:

The study will be a prospective experimental controlled study.

Patients of the study:

From the vicinity of the ophthalmology outpatient clinic of Ain Shams University Hospital, 100 patients of both sexes with amblyopia will be enrolled to this study. Informed consents will be obtained from adult patients and children's parents.

Patients will be assigned randomly into two groups:

Group A: 50 patients will receive the gold standard occlusion therapy

Group B: 50 patients will receive dichoptic treatment in the form of playing a video game (Lazy Eye Tetris games such as Lazy Eye Blocks ®) while wearing a red/green goggle.

Each group will be subdivided according to age:

1. From 4 to 7 years.
2. From above 7 to 12 years.
3. From above 12 to 30 years.

Hours of occlusion will be classified according to the degree of amblyopia:

- Mild to moderate amblyopia (Best corrected visual acuity (BCVA) < 0.2): 2-4 hours occlusion
- Severe (BCVA > 0.2): 4-6 hours occlusion

Hours of dichoptic treatment in group B will be classified according to the degree of amblyopia:

- Mild to moderate amblyopia (BCVA < 0.2): 2-4 hours of treatment
- Severe (BCVA > 0.2): 4-6 hours of treatment

Inclusion Criteria:

- Any degree of amblyopia
- Orthotropia in primary position.

Exclusion Criteria:

- Any ocular disease affecting vision
- Angle of deviation in primary position (Heterotropia)
- Adult patients and children's parents unwilling to enter or complete the study
- Ignorance of patients to use the video game

Methods

All patients will undergo the following:

- 1) Full medical and ophthalmic history
- 2) Examination:
 - A) External Appearance:
Anomalous Head Posture, globes (e.g., proptosis), lids (e.g. ptosis).
 - B) Refraction:
With and without cycloplegia.

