A Comparative Study between Dissociative Treatment and Binocular Interactive Treatment in Amblyopia

Thesis

Submitted to Faculty of Medicine – Ain Shams University
In Partial Fulfillment of the Requirements of Doctorate Degree in Ophthalmology
By

[name]

M.B,B.C.h (2009) , M.Sc (2014) ,

Faculty of medicine - Ain Shams University

Under supervision of

[name]. [name]

Professor of Ophthalmology
Faculty of medicine – Ain Shams University

[name]. [name]

Professor of Ophthalmology
Faculty of medicine – Ain Shams University

[name] [name]

Lecturer of Ophthalmology
Faculty of medicine – Ain Shams University

[name] [name]

Lecturer of Ophthalmology
Faculty of medicine – Ain Shams University

Faculty of medicine
Ain Shams University
Cairo – Egypt
2017

STATISTICAL ANALYSIS PLAN

Using the SPSS (or the Minitab or Mega Stat) statistical software, the data will be examined using standard summary statistics which will include, where appropriate, 95% confidence intervals.

A one-way analysis of variance (ANOVA) will be performed on the visual acuity data to determine whether there appeared to be an effect of measurement time on visual acuity, and pairwise comparisons of mean will then be performed, examining the changes from baseline to 1 month, 3 months and 6 months after treatment start.

An improvement of ≥ 0.125 LogMAR units will be considered clinically significant. In addition, the proportion of change will be calculated at 1 month, 3 months and 6 months follow up as follows (using the formula described by Stewart et al)

$$\text{Proportion of change} = \frac{VA_{as} - VA_{ae}}{VA_{as} - VA_{fe}}$$

Where VA_{as} is the vision of amblyopic eye at baseline, VA_{ae} is the vision of amblyopic eye at the end of the treatment (i.e. 6months) and VA_{fe} is the vision of the non-amblyopic eye at the end of the treatment.

Also percentage of compliance with treatment in each group will be measured as a secondary outcome measure.

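### The SAP specifies no between-arm acuity analysis, and comparing the arms on raw change would give up precision that a continuous baseline-acuity covariate would recover

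*SAP*

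**What the plan says.** SAP, paragraph 2: a one-way ANOVA is run on acuity "to determine whether there appeared to be an effect of measurement time on visual acuity", followed by pairwise comparisons of means, "examining the changes from baseline to 1 month, 3 months and 6 months after treatment start". Time is the only factor named.

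SAP, paragraph 3: the threshold is also on the raw-change scale: "An improvement of ≥ 0.125 LogMAR units will be considered clinically significant". A scaled measure is added: "In addition, the proportion of change will be calculated at 1 month, 3 months and 6 months follow up". It is (VAas − VAae)/(VAas − VAfe). The definitions begin "Where VA_{as} is the vision of amblyopic eye at baseline"; the other two terms, including the fellow eye's acuity, are taken when treatment ends. No test is attached to this measure.

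Protocol, Patients and Methods: "100 patients of both sexes with amblyopia will be enrolled to this study", and "Patients will be assigned randomly into two groups", 50 in each. The aim is to compare occlusion with dichoptic treatment. Entry is open to "Any degree of amblyopia", and the age bands run from 4 to 30 years. Baseline acuity sets the hours of treatment. It is not named as a stratification factor or as a covariate.

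Neither document gives a between-arm test, a baseline-adjusted model, an SD, a baseline/follow-up correlation, an effect size or a power.

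**The concern.** The trial exists to compare two randomised groups, so a Group A versus Group B comparison has to be made even though none is written down. The acuity quantity that the SAP prepares for testing is raw change, and that would be the natural one to carry into the comparison.

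A raw change score fixes the slope of follow-up acuity on baseline acuity at exactly 1. If badly affected eyes gain more than mildly affected ones, the true slope is below 1, and part of the baseline spread stays in the error of the between-arm difference. With every severity admitted, that spread may be considerable. At stake is the width of the confidence interval for the treatment difference, and so the chance of detecting a real one with a fixed 100 patients.

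**Working it through.** **Inputs from the documents.** 50 patients per group, randomised; raw change and the 0.125 LogMAR threshold; no covariate. All SDs, correlations, slopes and differences below are assumptions.

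**The plan's own figure.** The 100 patients come with no stated derivation, so there is nothing to reproduce and no basis for calling the number wrong.

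**Equal SDs at baseline and follow-up.** Let s be the SD and ρ the baseline/follow-up correlation. Per patient, the variance entering the between-arm contrast is

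- raw change: 2s²(1 − ρ)
- ANCOVA: s²(1 − ρ²)
- ratio: (1 + ρ)/2

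The fourth column multiplies the ratio by 1 + 1/(100 − 4) = 1.0104, the cost of estimating one covariate. The fifth is 50 divided by the ratio. The last is illustrative power for an assumed 0.10 LogMAR difference with s = 0.3 and two-sided 5% alpha.

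| ρ | Change / ANCOVA variance (units of s²) | Ratio | Ratio with covariate cost | Per group on raw change to match 50 with ANCOVA | Power, change → ANCOVA |
|---|---|---|---|---|---|
| 0.5 | 1.00 / 0.75 | 0.75 | 0.758 | 66.7 | 38.5% → 48.6% |
| 0.7 | 0.60 / 0.51 | 0.85 | 0.859 | 58.8 | 57.6% → 64.6% |
| 0.8 | 0.40 / 0.36 | 0.90 | 0.909 | 55.6 | 75.0% → 79.3% |
| 0.9 | 0.20 / 0.19 | 0.95 | 0.960 | 52.6 | 96.1% → 96.9% |

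A simulation of 4,000 trials at each of ρ = 0.5, 0.7 and 0.9 gave ratios of 0.758, 0.845 and 0.959. Both methods recovered the assumed 0.10 difference (means 0.0998 to 0.1016), so neither is biased.

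**Gain that rises with the deficit.** Suppose gain = p × starting deficit + residual, with fellow-eye acuity treated as constant. The slope on baseline is then 1 − p, and

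- variance of change = (p·SD0)² + SDe²
- ANCOVA variance = SDe²

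| p | SD0 | SDe | Variance of change | Ratio |
|---|---|---|---|---|
| 0.1 | 0.20 | 0.15 | 0.0004 + 0.0225 | 0.98 |
| 0.1 | 0.30 | 0.12 | 0.0009 + 0.0144 | 0.94 |
| 0.3 | 0.20 | 0.15 | 0.0036 + 0.0225 | 0.86 |
| 0.5 | 0.25 | 0.15 | 0.0156 + 0.0225 | 0.59 |
| 0.6 | 0.30 | 0.12 | 0.0324 + 0.0144 | 0.31 |

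In the p = 0.5 row the SD falls from √0.0381 = 0.195 to 0.150. The 95% half-width, t(98) × SD × √(2/50), falls from 0.077 to 0.060 LogMAR. The last row is extreme: it requires the SD of acuity to shrink from 0.30 at baseline to √((0.4 × 0.30)² + 0.12²) = 0.17 at follow-up.

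**Within one group.** Adjusting a group's mean change for baseline, evaluated at that group's own mean baseline, returns the same mean change. Its standard error in the p = 0.5 row is 0.195/√50 = 0.0276 either way. A regression would print 0.150/√50 = 0.0212, but only by treating the observed baseline mean as fixed. The saving therefore exists only in the difference between arms.

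**Cost of the covariate.** It is 1.0104 at 100 patients, with break-even near ρ = 0.98. In an age subgroup of about 33 (an assumed equal three-way split) it is 1 + 1/(33 − 4) = 1.0345, with break-even near ρ = 0.93.

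**The case against.** The strongest reply is that the criticism is aimed at an analysis that is not there. A reader might infer that the SAP judges treatment by raw change. The documents do not support that: the ANOVA factor is time, the pairwise comparisons are between time points, and there is no treatment-effect error term to which a covariate could be added. This stands. The missing between-arm comparison is the larger gap, and baseline adjustment is one choice in filling it. A reader might also infer that the planned mean changes are themselves less precise than they could be; the within-group step above shows that they are not.

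Read literally, a one-way ANOVA over time also ignores that the same patients are measured repeatedly. It overstates the variance of a mean change by 1/(1 − ρ), which is 2-fold at ρ = 0.5 and 5-fold at 0.8. That is a bigger loss, and its remedy is a repeated-measures model. This also stands. But correcting it alone leads to paired changes, and comparing the arms on those leaves the loss described here.

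It can be said that the proportion of change already deals with baseline severity. It does show that raw change is not the only planned measure. Its denominator, however, sets the amblyopic eye's baseline against the fellow eye's final acuity, so it is not the starting gap between the eyes. It is a ratio with no planned test, and it does not replace a covariate.

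Finally, the size is assumed. It is tempting to quote the p = 0.5 row as worth about 69% more patients (1/0.59 = 1.69). Nothing in the documents fixes p there. The protocol's introduction says that occlusion works less well in older children and adults, and enrolment runs to age 30, so a high p throughout is not supported.

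**Conclusion.** The point holds in a limited form. No between-arm acuity analysis and no baseline covariate are specified, and comparing the groups on raw change would leave usable precision behind. With equal SDs and ρ between 0.5 and 0.9, the variance saving is 5% to 25% before the roughly 1% cost of the covariate. It is larger if gain depends strongly on the starting deficit, and about 2% to 6% in the p = 0.1 rows. The direction is secure unless ρ is close to 1; the size rests wholly on assumed SDs, correlations and slopes.

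A reader might go further and call the raw-change comparison biased. Under randomisation it is not. A chance baseline difference shifts the estimate in a single trial, but that is the same imprecision already counted above. The protocol's exclusion of patients who do not complete follow-up could weaken the protection of randomisation, and a baseline covariate would not be a remedy for that.

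The change should be made, as part of writing the between-arm analysis that is missing.

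**What to change.** In SAP paragraph 2, specify the between-arm analysis:

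- **Outcome:** amblyopic-eye LogMAR acuity at 6 months, or at all follow-up visits in a repeated-measures model with arm, time and arm-by-time terms.
- **Covariate:** baseline amblyopic-eye LogMAR acuity, continuous. In the repeated-measures version the baseline value enters only as a covariate, not also as an outcome.
- **Report:** the adjusted Group A minus Group B difference with its 95% CI.
- **Descriptive only:** raw changes from baseline and the proportion of change.

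Two details need settling in the same edit. The protocol (Methods, item C) records Snellen acuity or preferential looking, so the conversion to LogMAR should be stated; the SAP's outcome needs it anyway. The intermediate visit is at 2 months in the protocol and 3 months in the SAP, and the two must be reconciled before an all-visits model is written. The 6-month visit is in both.

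The cost is a few sentences and one degree of freedom: about 1% of variance at 100 patients and about 3% in an age subgroup of about 33. Baseline acuity is already collected, so no visits or patients are added.

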 - C) Visual acuity:
With and without correction using Snellen acuity chart and preferential looking test for non-verbal patients.
 - D) Motility:
Ductions and versions (9 positions of gaze)
 - E) Angle of deviation if any
 - F) Fixation :
Fixation behavior (fixation preference) will be tested via base down 10 PD fixation preference test.
 - G) Quantitative Binocular vision assessment
 - H) Anterior segment examination.
 - I) Posterior segment examination using indirect ophthalmoscopy with a 20-D (diopter) lens through a dilated pupil.

All patients in Group A will receive the gold standard occlusion therapy. All patients in Group B will receive dichoptic treatment

Treatment assessment:

All patients will be followed up in the following schedule: after 1 month, after 2 months and after 6 months with regards to visual acuity. Patients who fail to complete the full time of the follow up period will be excluded from the study.

References:

- 2) Aldebasi YH. Prevalence of amblyopia in primary school children in Qassim province, Kingdom of Saudi Arabia. *Middle East Afr J Ophthalmol.* 2015;**22**(1):86-91
- 3) American Academy of Ophthalmology Basic and Clinical Science Course Subcommittee. Basic and Clinical Science Course. Pediatric Ophthalmology and Strabismus: Section 6. San Francisco, CA: American Academy of Ophthalmology. 2012.pp.61.
- 7) Birch EE. Amblyopia and binocular vision. *Progress in retinal and eye research* 2013;**33**:67-84

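### The SAP analyses acuity at 3 months where the protocol measures it at 2 months, and its proportion-of-change formula uses 6-month acuity at every visit

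*SAP*

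**What the plan says.** The protocol's Treatment assessment section sets follow-up "after 1 month, after 2 months and after 6 months with regards to visual acuity".

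The SAP's second paragraph plans an ANOVA for an effect of measurement time on acuity, then pairwise comparisons of means "examining the changes from baseline to 1 month, 3 months and 6 months after treatment start". Its third paragraph sets a threshold for improvement ("0.125 LogMAR units will be considered clinically significant") and adds that "the proportion of change will be calculated at 1 month, 3 months and 6 months follow up".

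The formula is (VA_as − VA_ae) / (VA_as − VA_fe). The SAP defines its three terms as follows:

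- VA_as "is the vision of amblyopic eye at baseline"
- VA_ae "is the vision of amblyopic eye at the end of the treatment (i.e. 6months"
- VA_fe "is the vision of the non-amblyopic eye at the end of the treatment"

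**The concern.** There are two separate faults, and both fall on the interim visits.

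First, the two documents disagree on the month of the intermediate visit. Acuity is the only measure that the protocol's Treatment assessment section names, and there are only three follow-up points. An analyst cannot follow both documents at the middle one.

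Second, the proportion of change is requested at three visits from a formula that contains no visit-specific term. If the definition is followed, the 1-month and intermediate values repeat the 6-month value. They overstate early response in an eye that is still improving, understate it in an eye that later regresses, and carry no information on how quickly either treatment works.

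**Working it through.** The plan states no figure to reproduce here. The check compares the texts and then substitutes into the SAP's formula.

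**Visit months**

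| Month | Protocol, Treatment assessment | SAP, mean contrasts | SAP, proportion of change |
|---|---|---|---|
| 1 | yes | yes | yes |
| 2 | yes | no | no |
| 3 | no | yes | yes |
| 6 | yes | yes | yes |

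Months 1 and 6 agree. Month 2 is only in the protocol and month 3 is only in the SAP, where it appears twice. Reading the protocol's schedule as successive intervals does not reconcile them: 1 + 2 = 3 months fits, but 3 + 6 = 9 months does not match the SAP's last visit at 6 months. Neither document contains other text that explains the difference.

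**Formula**

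Write VA_ae(t) for amblyopic-eye acuity at visit t.

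- Literal definition, at any visit: P_lit = (VA_as − VA_ae(6)) / (VA_as − VA_fe). Nothing depends on t.
- Visit-specific definition: P(t) = (VA_as − VA_ae(t)) / (VA_as − VA_fe).
- Difference: P_lit − P(t) = (VA_ae(t) − VA_ae(6)) / (VA_as − VA_fe).

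In logMAR, lower is better. With a positive denominator, the difference is therefore positive if the eye improves after visit t, negative if it regresses, and zero if it does not change. At t = 6 it is zero by construction.

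**Size, as an illustration.** The documents give neither the expected change after an interim visit nor the denominator. I take a change of 0.125 logMAR, borrowed from the SAP's threshold, and assume a range for the denominator.

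| Assumed VA_as − VA_fe (logMAR) | 0.125 / denominator | Error in interim proportion |
|---|---|---|
| 0.2 | 0.625 | ±0.63 |
| 0.4 | 0.3125 | ±0.31 |
| 0.6 | 0.208 | ±0.21 |
| 0.8 | 0.156 | ±0.16 |

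**Check of sign.** Assume baseline 0.60, fellow eye 0.00 and 6-month acuity 0.30. The literal value is (0.60 − 0.30) / 0.60 = 0.50 at every visit.

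| Assumed VA_ae(t) | Visit-specific proportion | Literal minus visit-specific |
|---|---|---|
| 0.425 (improves later) | 0.175 / 0.60 = 0.292 | +0.208 |
| 0.300 (no change) | 0.300 / 0.60 = 0.500 | 0 |
| 0.175 (regresses later) | 0.425 / 0.60 = 0.708 | −0.208 |

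**A steadily improving eye.** Assume baseline 0.70, then 0.60, 0.50 and 0.40 at the first, intermediate and 6-month visits, with fellow eye 0.00. The visit-specific proportions are 0.10/0.70 = 0.143, 0.20/0.70 = 0.286 and 0.30/0.70 = 0.429. The literal formula gives 0.429 at all three.

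**The case against.** The strongest reply concerns the formula. Three identical numbers would make the request for three time points pointless, so a sensible analyst would put in the acuity at each visit and treat the definition as describing the final calculation only. That is probably what was intended. But the SAP ties the term explicitly to 6 months, so the analyst would have to override the written definition.

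On the visit month, acuity will be collected at some intermediate visit either way, and the ANOVA can be run on whatever visits exist. That is true, but the planned contrast names a month at which nothing is scheduled, and the text gives no basis for choosing between 2 and 3.

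Three further points stand as limits:

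- The size figures are illustrative. The 0.125 is a threshold for improvement, not an expected change after an interim visit, and the largest error pairs it with the smallest assumed denominator.
- The proportion of change is a supplementary measure, and the 6-month results are untouched.
- Holding the fellow eye at the end of treatment may be a deliberate reference level. The SAP attributes the formula to a source outside the documents, so the sponsor should confirm that term as well.

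**Conclusion.** Both parts hold on the current text. One of three follow-up months differs between the documents, which leaves the SAP's 3-month outputs without a scheduled measurement and the protocol's 2-month visit without a named contrast. The formula as defined returns the 6-month proportion at every visit, so its interim values are wrong whenever acuity at that visit differs from acuity at month 6.

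The algebra needs no assumption. The range of 0.16 to 0.63 in either direction rests on an assumed later change of 0.125 logMAR and assumed denominators of 0.8 down to 0.2 logMAR; it does not predict the error in this trial. The mean changes at 1 and 6 months and the 6-month proportion are correct as planned. This should be corrected, but it does not threaten the 6-month acuity result.

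**What to change.** 1. The sponsor confirms whether the intermediate visit is at month 2 or month 3, and uses that month in the protocol's Treatment assessment section and in both places in the SAP.
2. The SAP redefines VA_ae as the acuity of the amblyopic eye at the visit being analysed, and keeps VA_fe at the end of treatment as now stated, with the sponsor confirming that this is intended: proportion at visit t = (VA_as − VA_ae(t)) / (VA_as − VA_fe). At month 6 this equals the present formula.

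The cost is a wording change to one visit month, in either the protocol or the SAP, and to one symbol definition in the SAP. No visits or measurements are added.

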Several modalities of treatment for amblyopia are available, yet occlusion treatment is the gold standard involving covering the good eye with a patch for a prescribed period of time ranging from 10 minutes daily to all waking hours **(Von Noorden and Campos, 2002; Stewart et al., 2005)**. However, its effectiveness decreases in older children and adults **(Pediatric Eye Disease Investigator Group, 2005)**

Disadvantages include prolonged treatment leading to poor compliance, patching related distress, relationship strain and stigma. In extreme cases, non-compliance with patching results in a costly hospital admission to supervise the patching treatment. In addition, wearing a patch eliminates any advantage of binocularity **(Dixon-Woods et al., 2006)**. Not to mention that not all patients respond to patching and of those who do, many have residual amblyopia after treatment is stopped regardless of compliance **(Hess et al., 2014)**. More importantly, binocular vision is not automatically restored once the vision in the amblyopic eye has been improved. In fact, once

the patch is removed after therapy, the amblyopic eye could be suppressed by the better seeing eye and can lose some of the gains achieved as a result of therapy. **(Birch, 2013)**

Another modality of treatment is atropine eye drops and optical penalization which are usually secondary treatments to failed patching but carrying the same disadvantages as the ordinary patching **(Foss et al., 2013)**

Advances in amblyopia treatment include dichoptic training, perceptual learning, and video gaming **(Tsirlin et al., 2015)**. These depend on the fact that the adult brain has been shown to be much more plastic than it was once believed to be and hence have the advantage of expanding the age of response in adults. **(Pizzorusso et al., 2002; He et al., 2006)**

Perceptual learning approaches have the advantage of being a dichoptic (binocular treatment) approach which is independent of age and type of amblyopia. **(Polat et al., 2004; Levi and Li, 2009)** Furthermore, it has been shown recently that therapy promotes binocular vision by strengthening stereopsis and reducing suppression **(Hess et al., 2010; Hess et al., 2011)**

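### The proportion of change is scaled by the fellow eye's final acuity, so when the amblyopic eye improves, fellow-eye loss can raise the score, and no fellow-eye summary is explicitly specified to show it

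*SAP*

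**What the plan says.** The SAP first plans an ANOVA and pairwise changes from baseline on the acuity data, without naming an eye. It then sets a threshold: "An improvement of ≥ 0.125 LogMAR units will be considered clinically significant". As an addition to these, "the proportion of change will be calculated at 1 month, 3 months and 6 months follow up as follows", using a formula credited to a published source:

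PC = (VA_as − VA_ae) / (VA_as − VA_fe)

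Here VA_as is the amblyopic eye's acuity on entry, and VA_ae is that eye's acuity when treatment ends, which the SAP equates with month 6. The fellow-eye term, VA_fe, is defined separately: it "is the vision of the non-amblyopic eye at the end of the treatment". The only other outcome named is compliance.

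The Protocol's introductory text describes occlusion as "covering the good eye with a patch". Under 'Patients of the study', occlusion is given to Group A (50 patients), while Group B (50 patients) plays a video game through red/green goggles. Under 'Treatment assessment', follow-up is "after 1 month, after 2 months and after 6 months with regards to visual acuity", again with no eye named.

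**The concern.** The ratio is meant to express how much of the initial deficit was corrected. Its denominator, however, contains a quantity measured after treatment that treatment may itself change. If the fellow eye ends worse than it began, the apparent deficit shrinks and the same amblyopic-eye gain counts for more. One arm works by covering that eye and the other does not, so the effect need not be equal in the two arms. Someone reading only the ratio could not separate amblyopic-eye gain from fellow-eye loss. At stake is a fair comparison on this index and the visibility of a possible harm.

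**Working it through.** **Inputs.** The formula and the definitions of its terms come from the SAP. LogMAR (higher is worse) is inferred from the SAP's threshold; the Protocol's chart is Snellen. The documents give no worked value of the ratio and no rate of fellow-eye loss, so there is no stated figure to reproduce. All acuities and loss rates below are assumptions, with the fellow eye at 0.0 logMAR at baseline.

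**Direction.** With the amblyopic-eye result held fixed, dPC/dVA_fe = (VA_as − VA_ae) / (VA_as − VA_fe)². This is positive whenever the amblyopic eye improved.

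**Size for one patient.**

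| Amblyopic eye (logMAR) | Final fellow eye 0.0 | 0.1 | 0.2 |
|---|---|---|---|
| 1.00 to 0.70 | 0.30/1.00 = 0.300 | 0.30/0.90 = 0.333 | 0.30/0.80 = 0.375 |
| 0.60 to 0.30 | 0.30/0.60 = 0.500 | 0.30/0.50 = 0.600 | 0.30/0.40 = 0.750 |
| 0.30 to 0.175 | 0.125/0.30 = 0.417 | 0.125/0.20 = 0.625 | 0.125/0.10 = 1.250 |

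The last row is a gain of exactly the SAP's threshold. The distortion is largest in mild amblyopia, where the denominator is small, and the Protocol's inclusion criteria admit any degree.

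**Where it does not arise.** If the amblyopic eye is unchanged, PC = 0 whatever the fellow eye does. If it worsens from 0.60 to 0.70, a fellow-eye loss of 0.1 moves PC from −0.10/0.60 = −0.167 to −0.10/0.50 = −0.200, which is a penalty. If the fellow eye instead gains 0.1, the 0.60 to 0.30 patient falls from 0.500 to 0.30/0.70 = 0.429.

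**Check on a decimal scale.** For 0.25 to 0.50 with a final fellow eye of 1.0, 0.8 and 0.63, PC = 0.333, 0.455 and 0.658. The direction is the same.

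**Shift in the Group A mean.** For the 0.60 to 0.30 case, 10% of patients losing 0.1 gives 0.10 × (0.600 − 0.500) = 0.01; 20% losing 0.2 gives 0.20 × (0.750 − 0.500) = 0.05. The same rates give about 0.003 to 0.015 if every patient followed the first row (0.10 × 0.033; 0.20 × 0.075), and about 0.02 to 0.17 if every patient followed the last (0.10 × 0.208; 0.20 × 0.833).

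A simulation with spread in baseline and gain (mean gain 0.2, SD 0.1; mean baseline 0.6 or 0.4) and a fellow-eye loss of 0.1 in 10% to 20% of patients gave shifts of 0.008 to 0.016 at baseline 0.6 and 0.018 to 0.037 at baseline 0.4. The SD of the ratio between patients was about 0.20 and 0.29 respectively.

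**With the baseline fellow eye in the denominator.** The 0.60 to 0.30 patient scores 0.50 whether the fellow eye loses 0, 0.1 or 0.2.

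**The case against.** The strongest case against runs as follows.

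- **The index is supplementary.** It is introduced as an addition to change from baseline and the 0.125 LogMAR criterion. Neither that criterion nor amblyopic-eye change contains VA_fe, so an inflated ratio could be seen against them. The SAP also names no test of the ratio between arms; that use is inferred from the Protocol's aim. This stands, and it limits the importance of the point.
- **The final fellow eye is a defensible reference.** It allows for maturation over six months in children from age 4. The formula is credited to a published source that is not available here, so no departure from that source can be claimed. This also stands: the case for replacing the published version outright is not made.
- **No arm difference is shown.** A reader might infer that the ratio is biased in favour of occlusion. The documents do not support that: they give no rate of fellow-eye loss in either arm, and they do not say that dichoptic play leaves the fellow eye unchanged. The loss rates used above are assumptions.
- **The omission is not absolute.** A reader might also infer that fellow-eye change will go unreported. The planned summaries and ANOVA cover acuity data with no eye named, so they could include the fellow eye. What can be said is that no fellow-eye summary is explicitly specified.

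The algebra survives all of this: a post-treatment value sets the scale of benefit, and the plan does not require the table that would show when this matters.

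**Conclusion.** The point holds in a limited form. When the amblyopic eye has improved, fellow-eye loss raises the proportion of change with no added benefit: from 0.50 to 0.60 or 0.75 in the 0.60 to 0.30 example for losses of 0.1 or 0.2 logMAR. Fellow-eye loss is not rewarded in every patient, since the effect needs some amblyopic-eye gain.

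For single patients the effect can be large, most of all in mild amblyopia. On an arm mean it is probably small if loss is uncommon: about 0.01 to 0.05 for the worked case at 10% to 20% losing 0.1 to 0.2 logMAR, and more if most patients are mild. The actual difference between arms is unknown. It would not be right to conclude that the trial's efficacy analysis as a whole is compromised, because the 0.125 LogMAR criterion does not involve the fellow eye. This is a worthwhile, low-cost improvement.

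**What to change.** 1. Keep the published ratio as planned.
2. Add a sensitivity version with baseline fellow-eye acuity as VA_fe, and show both by arm.
3. Tabulate fellow-eye acuity change from baseline by arm, at 6 months at least and at earlier visits where it is measured, with the number of fellow eyes worsening by 0.125 logMAR or more.
4. State which eye each acuity analysis uses.

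**Cost.** One derived variable and one table. The 6-month fellow-eye acuity is already needed for the published ratio. Baseline acuity is part of the entry examination (Protocol, 'Methods', item C), although the eye is not named there, so the plan should say that both eyes are recorded. Earlier fellow-eye values are less certain: the SAP wants the ratio at 1 and 3 months but defines its terms only at the end of treatment, and the Protocol's second visit is at 2 months. Those passages need to be reconciled before earlier visits are tabulated.

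**Downside.** Two versions of the ratio must be explained, and the baseline version does not allow for fellow-eye maturation in young children. That is why it belongs beside the published ratio as a sensitivity analysis.
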